Expected effect:	ENDOANGEL's intended use is to effectively improve the quality of EUS scanning for physicians, enhance the cognitive ability of endoscopists in endoscopic ultrasound images, and reduce the missed diagnosis of lesions.
Primary Endpoint:	Missed scanning rate of adjacent important anatomical structures in pancreatic endoscopic ultrasonography
Secondary Endpoints:	
 1.Pancreatic lesions detection rate; 2.Cholangiopancreatic duct lesions detection rate 3.The average number of scanning in the pancreatic standard station of endoscopic ultrasonography 4.Detection rate of lesions in different pancreatic standard stations of endoscopic ultrasonography 5.Missed scanning rate of adjacent vital anatomical structures in different pancreatic standard stations of endoscopic ultrasonography 6.Mean scanning time in different pancreatic standard stations of endoscopic ultrasonography
Trail design:	Prospective, single-center, randomized controlled trial
Participants:	Male and female subjects aged 18 years or older will require a endoscopic ultrasonography, and voluntarily provide endoscopic ultrasonography imaging data and sign an informed consent form.
Sample size:	285 samples needed to be enrolled
Study Process:	Subjects who met all inclusion criteria and did not meet all exclusion criteria were included in the study before endoscopic ultrasonography. All included subjects signed an informed consent form. Subjects will be randomized prior to the start of the examination to either an Endoangel-assisted experimental group or a control group without Endoangel assistance. The operating physician completed the endoscopic ultrasonography according to the presence or absence of AI prompt. The recorder shall record the number of adjacent important structures, the number of standard stations, the operation time and the lesion detection etc. Follow-up will be performed for one week after the end of examination. The end time of follow-up is the end time of study. And the results are sent to an independent data analysis team for review.

[figure not shown]

Security	Safety incidents shall be evaluated and reported according to the quality management measures for clinical trials of medical devices
-----------------	--

1.1. Time and Event Tables

Events	Screening period (d -30 [~] -1)	The day of EUS (d 0)	Follow up (d 1-14)
Informed Consent	X		
Basic characteristics	X		
Medical history/surgical history	X		
Inclusion/Exclusion Criteria	X		
Random		X	
Endoscopic Ultrasonography		X	
Concomitant treatment	X	X	
Concomitant medication	X	X	
Adverse Events		X	X
Research completed			X

1.2. Flow chat

2. Introduction

Pancreatic cancer is a malignant tumor of the digestive system with insidious onset, rapid progression and very poor prognosis[1, 2]. According to the latest cancer data in China in 2020 released by the International Agency for Research on Cancer (IARC) of the World Health Organization, there are about 120,000 new cases of pancreatic cancer in China, with a mortality rate close to 100%, which seriously endangers the national health[3, 4]. Early diagnosis of pancreatic cancer can be achieved by surgical resection with a 5-year survival rate of 58% [5], Once advanced pancreatic cancer develops, patient survival is 7.2%[6]. As a rapidly developing deadly cancer, missed diagnosis of pancreatic cancer may have extremely serious consequences for patients. How to improve the diagnostic rate of early pancreatic cancer is an urgent problem to be solved.

EUS(endoscopic ultrasonography) is considered one of the most sensitive modalities for pancreatic cancer detection. It has a much higher diagnostic accuracy than MRI and CT for the diagnosis of pancreatic cancer, especially early pancreatic cancer < 1 cm in diameter (EUS-FNA 95.6% vs CT 77.4%, MRI 76.2%)[7-9]. EUS is the modality of choice for the early diagnosis of pancreatic tumors[10]. To avoid a missed diagnosis of the pancreatic cancer, the continuity and integrity of EUS needs to be ensured as much as possible. But EUS is highly operator-dependent and the learning curve is steep, and the quality of the examination is highly dependent on the operator's technique[11-13]. Therefore, it is necessary to develop a system that can effectively assist the full scanning of EUS.

The station approach in pancreatic EUS has been established as the standard scanning procedure[14-15]. The principle of completing the station approach is to find the anatomical landmarks of this station[16-17], Such as organs (kidney, spleen), blood vessels (such as splenic artery, splenic vein, portal vein), ducts (pancreatic duct, bile duct), etc. The scanning of these anatomical landmarks is the basis for an accurate assessment of the entire pancreas.

At the same time, the type of pancreatic lesions and the development of the course have abnormal imaging findings of different anatomical structures[18-19]. For example, ultrasound images of pancreatic cancer will show vascular invasion, deformation of the biliopancreatic duct, and metastasis of adjacent organs[20]. The guidelines clearly require that the choice of surgical approach for pancreatic cancer needs to be based on the degree of invasion of the cancer to adjacent important anatomical structures, to maximize the volume sparing of functional pancreatic parenchyma[21]. Complete anatomical scanning can assist in the diagnosis of pancreatic lesions and guide patient treatment and prognosis.

In recent years, artificial intelligence (AI) has been successfully applied in multiple medical fields[22-24]. At present, there have been studies of AI-based endoscopic ultrasonography for the identification of pancreatic lesions[25-27], However, there are no studies of AI-based navigation system for pancreatic endoscopic ultrasonography. Previously, we have successfully developed a standard station scanning navigation system for the pancreas and bile ducts. This system can improve the recognition accuracy of endoscopists for standard stations and enhance the cognitive ability of endoscopic ultrasonography images[28-29].

Based on the previous, we constructed a deep learning-based pancreatic scanning navigation system in EUS, which can assist in identifying important anatomical structures adjacent to the pancreas in real time. and verify its auxiliary performance for endoscopists in clinical practice. In order to improve the quality of EUS and reduce the missed diagnosis of pancreatic lesions.

3. Patient Selection

Male and female subjects aged 18 years or older will require a endoscopic ultrasonography, and voluntarily provide endoscopic ultrasonography imaging data and sign an informed consent form.

Patients not meeting the inclusion criteria or meeting exclusion criteria will not be considered for participation in the study. Patients who met all criteria and signed informed consent may be excluded from the study due to:

- Endoscopists' professional advices/medical reasons (only under very limited conditions to avoid researcher bias).
- Withdraw informed consent.

3.1. Inclusion criteria

All patients meeting the following criteria will be considered for participation in the study:

- 1) Male or female aged 18 or above;
- 2) EUS is needed to further clarify the characteristics of digestive tract diseases;
- 3) Patients able to give informed consent were eligible to participate.
- 4) Able and willing to comply with all study process.

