3.2. Exclusion criteria

All patients meeting the following criteria will not be considered for participation in the study:

- 1) Has participated in other clinical trials, signed informed consent and was in the follow-up period of other clinical trials.
- 2) Has participated in clinical trials of the drug and is in the elution period of the experimental drug or control drug.
- 3) Drug or alcohol abuse or psychological disorder in the last 5 years.
- 4) Patients in pregnancy or lactation.
- 5) A history of Upper Gastrointestinal surgery.
- 6) Patients with anatomical abnormalities of the upper gastrointestinal tract due to advanced neoplasia
- 7) Patients in whom the presence of clearly defined vital anatomical structures cannot be observed
- 8) Researchers believe that the patient is not suitable to participate in the trial.

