4.1. Primary Endpoint

1) Missed scanning rate of adjacent important anatomical structures in pancreatic endoscopic ultrasonography:

It was calculated by dividing the number of important anatomy that is not scanned in the actual EUS pancreas by the number of EUS.

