4.2. Secondary Endpoints

- 1) Pancreatic lesions detection rate: It was calculated by dividing the total number of patients being detected pancreatic lesions by the number of EUS.
- 2) Cholangiopancreatic duct lesions detection rate: It was calculated by dividing the total number of patients being detected cholangiopancreatic duct lesions by the number of EUS.
- 3) The average number of scanning in the pancreatic standard station of endoscopic ultrasonography: It was calculated by dividing the total number of scanning in the pancreatic standard station by the number of EUS.
- 4) Detection rate of lesions in different pancreatic standard stations of endoscopic ultrasonography: It was calculated by dividing the number of patients with pancreatic lesions and Cholangiopancreatic duct lesions in the different standard stations by the number of EUS.
- 5) Missed scanning rate of adjacent vital anatomical structures in different pancreatic standard stations of endoscopic ultrasonography: It was calculated by dividing the number of important anatomy that is not scanned in the different standard stations by the number of EUS.
- 6) Mean scanning time in different pancreatic standard stations of endoscopic ultrasonography: It was calculated by dividing the total scanning time by the number of EUS.

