6.2.2. Patient Selection

All patients who underwent EUS, agreed to use EndoAngel and generally meet the study requirements were screened based on the inclusion/exclusion criteria. Patients who passed the screening were enrolled and recorded in the subject screening and enrollment tables. There is no bias in the choice of the enrolled subjects. The date of screening, the results (enrolled or not), and the primary reason for not selecting subjects (such as not meeting inclusion criteria, or not interested in participating in the study) will be recorded.

After the patients are enrolled, the research center should complete the preoperative study data collection.

It is desirable to be able to collect complete data for all enrolled patients, without those withdrawal from the study.

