6.3.3 Intraoperative Managements

- 1) Patient position: lateral position with appropriate restraint.
- 2) Insertion route: according to the actual situation of the subject, usually through the esophagus
- 3) Routine observation

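### Inclusion criterion 2 does not require a planned pancreatic scan, although every efficacy endpoint is pancreatic or biliopancreatic and is divided by all EUS examinations

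*Combined protocol and SAP*

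**What the plan says.** All references are to the combined protocol and SAP.

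- **Who enters.** Section 3.1, item 2, asks only that "EUS is needed to further clarify the characteristics of digestive tract diseases". The synopsis and the opening of section 3 are equally general, and section 6.2.2 states: "All patients who underwent EUS, agreed to use EndoAngel and generally meet the study requirements were screened based on the inclusion/exclusion criteria". None of these names a pancreatic or biliary indication.
- **Who is kept out.** The nearest exclusions in section 3.2 are item 7, "Patients in whom the presence of clearly defined vital anatomical structures cannot be observed", and item 8, "Researchers believe that the patient is not suitable to participate in the trial". The first is about whether structures can be seen. The second is open discretion. Neither concerns the purpose of the examination.
- **What is done.** Section 6.3.3 covers position and insertion route and then says "Routine observation". It does not ask for a full set of pancreatic stations in each subject.
- **What is measured.** Section 4.1 names the primary endpoint "Missed scanning rate of adjacent important anatomical structures in pancreatic endoscopic ultrasonography" and calculates it by "dividing the number of important anatomy that is not scanned in the actual EUS pancreas by the number of EUS". The six endpoints in section 4.2 are also pancreatic or biliopancreatic with the same denominator. The first, for example, is obtained by "dividing the total number of patients being detected pancreatic lesions by the number of EUS".
- **How it is analysed.** Section 8.5 bases the main analysis on the per-protocol set. Section 6.5.2 blinds subjects and evaluators. The operator works with or without the AI prompt (synopsis) and so knows the arm.

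**The concern.** The entry rule and the endpoints describe different sets of examinations. A patient sent for EUS of, say, a gastric wall lesion meets section 3.1, but the examination may have no pancreatic aim. The plan does not say what happens to that patient in the primary endpoint, and there are two readings.

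1. **Literal calculation.** The patient had an EUS, so he or she is in the denominator, and the unscanned pancreatic structures are counted as missed. If this happens equally in both arms, the contrast between arms shrinks and power is lost.
2. **Reading by the endpoint's name.** Only pancreatic EUS counts, so the examination is left out. It would then be left out after randomisation, depending on what an operator who sees or does not see the prompts chose to do, and in a trial whose main analysis is already per protocol.

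There is also a question of meaning. Randomisation balances the indications between arms. It does not balance the decision to enter the pancreatic stations, which is taken afterwards and which a prompt may influence. If it does, the difference between arms mixes whether the pancreas was examined with how completely it was examined. Section 5.1 is about helping operators identify structures adjacent to the pancreas, which is closer to the second question.

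**Working it through.** **Inputs from section 8.4:** missed rate 20% (control) and 8% (experimental), two-sided alpha 5%, power 80%, dropout 10%. Allocation is 1:1 (section 6.5.1).

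**Step 1: the plan's own figure.** For two independent proportions with unpooled variance,

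n per arm = [p1(1−p1) + p2(1−p2)] × (1.960 + 0.842)² / (p1−p2)²

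= (0.1600 + 0.0736) × 7.85 / 0.0144 = 127.3, rounded up to 128.

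Total 256; 256 / 0.9 = 284.4, rounded up to 285. This is the stated sample size. It treats each patient as one binary outcome and assumes that every enrolled examination can show the 20% to 8% contrast.

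**Step 2: add examinations with no pancreatic aim.** Two assumptions are needed, and the document supplies neither:

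- f, the share of enrolled examinations with no pancreatic aim: 5%, 10% or 20%;
- m, the missed rate in those examinations, equal in both arms: 100%, 50% or 20%. The last value means no excess misses, only no device effect.

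Then

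- control rate = (1−f) × 20% + f × m
- experimental rate = (1−f) × 8% + f × m
- difference = (1−f) × 12 points, whatever m is.

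Example, f = 10% and m = 100%: control 0.9 × 20% + 10% = 28.0%; experimental 0.9 × 8% + 10% = 17.2%; difference 10.8 points.

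**Step 3: power with 128 evaluable per arm**, from the exact distribution of the two-sided chi-square test. With f = 0 it is 80.2%.

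| f | m | Control | Experimental | Difference (points) | Power |
|---|---|---|---|---|---|
| 5% | 100% | 24.0% | 12.6% | 11.4 | 66% |
| 5% | 50% | 21.5% | 10.1% | 11.4 | 71% |
| 5% | 20% | 20.0% | 8.6% | 11.4 | 75% |
| 10% | 100% | 28.0% | 17.2% | 10.8 | 54% |
| 10% | 50% | 23.0% | 12.2% | 10.8 | 62% |
| 10% | 20% | 20.0% | 9.2% | 10.8 | 69% |
| 20% | 100% | 36.0% | 26.4% | 9.6 | 38% |
| 20% | 50% | 26.0% | 16.4% | 9.6 | 47% |
| 20% | 20% | 20.0% | 10.4% | 9.6 | 57% |

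The formula of step 1 gives powers within one percentage point of these. By that formula, restoring 80% power at f = 10% would need a total of 365 (m = 20%) to 516 (m = 100%), dropout included, instead of 285.

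**Step 4: the direction is not fixed.** If prompts led operators to scan the pancreas in examinations where controls did not, the difference would grow. In the extreme case, with f = 10%, controls missing everything in those examinations and the experimental arm at 8% throughout, the rates are 28% and 8%, a difference of 20 points instead of 12. This shows only that the mixture can work the other way. The document gives no basis for its size.

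**The case against.** The strongest reply is that the study examination is meant to be a pancreatic EUS. The primary endpoint is named for it, the device is a pancreatic navigation system, section 2 describes the station approach as established practice for the pancreas, and the synopsis has a recorder log structures and stations in study examinations. Investigators could also use exclusions 7 and 8 before randomisation, so f may be small. At f = 2% with m between 20% and 50%, power would still be 77–78%.

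Much of this stands, and it limits the point. A reader might infer any of the following, and the document supports none of them:

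- **That such examinations do count as missed.** This is one reading. No scoring rule is given.
- **That control operators will skip the pancreas.** The short entry in section 6.3.3 is one item in a list. It does not license skipping.
- **That every efficacy endpoint scores completeness.** The lesion detection rates and the mean scanning time do not, although their denominators are affected.
- **That the type I error is inflated.** If the prompt makes operators scan structures that controls leave unscanned, the missed rate really is lower, which agrees with the first hypothesis in section 8.3. The effect would be broader than intended, but it would not be a false positive.
- **That 20% and 8% cannot describe the enrolled patients.** Section 8.4 gives no source population for these rates, so this cannot be judged.

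What the reply does not do is supply the missing condition. The intention has to be inferred from the endpoint's name, while the eligibility text in four places says something wider.

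**Conclusion.** The point holds as a gap between eligibility and endpoints, worth correcting because the correction is cheap. The entry rule admits patients whose examination need not show the contrast on which the sample size rests, and the plan does not say how they are scored.

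If they are enrolled and scored alike in both arms, the likely effect is dilution, with the power losses tabulated above. These rest on assumed values of f and m, on no device effect in those examinations, and on the plan's binary framing. Section 4.1 as written counts structures per EUS, so the percentages indicate size and do not describe that endpoint exactly. If the examinations are instead left out after randomisation, the risk is selection, which cannot be quantified here. Nor can the document settle how far prompting alters the decision to scan at all. A reader might infer a demonstrated distortion of the primary comparison; what is shown is an ambiguity that can cost power and blur what the difference means.

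**What to change.** Amend section 3.1, item 2, to require that a station-by-station EUS examination of the pancreas is planned whichever arm is assigned, and record that intention before randomisation. State in section 4.1 that all randomised patients with an EUS stay in the denominator, including those whose planned pancreatic scan is not completed, so that the operator's conduct after randomisation cannot decide who is counted. The plan's own inputs then apply to the enrolled patients, and the sample size of 285 need not change on this account.

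The cost is one line in section 3.1, one sentence in section 4.1 and one tick box before randomisation. Patients referred only for non-pancreatic lesions would not be enrolled, so recruitment may be slightly slower.

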3.2. Exclusion criteria

All patients meeting the following criteria will not be considered for participation in the study:

- 1) Has participated in other clinical trials, signed informed consent and was in the follow-up period of other clinical trials.
- 2) Has participated in clinical trials of the drug and is in the elution period of the experimental drug or control drug.
- 3) Drug or alcohol abuse or psychological disorder in the last 5 years.
- 4) Patients in pregnancy or lactation.
- 5) A history of Upper Gastrointestinal surgery.
- 6) Patients with anatomical abnormalities of the upper gastrointestinal tract due to advanced neoplasia
- 7) Patients in whom the presence of clearly defined vital anatomical structures cannot be observed
- 8) Researchers believe that the patient is not suitable to participate in the trial.

3.3. Definition of enrollment

After participants signed informed consent, they were randomized before the endoscopic ultrasonography. The randomization time was the enrollment time, and was recorded in CRF.

4. Endpoints

4.1. Primary Endpoint

1) Missed scanning rate of adjacent important anatomical structures in pancreatic endoscopic ultrasonography:

It was calculated by dividing the number of important anatomy that is not scanned in the actual EUS pancreas by the number of EUS.

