8.4. Sample Size Calculation

We mainly studied the effect of EndoAngel on the quality of EUS scanning for physicians. Therefore, data collection and analysis were conducted for the main effect. It is expected that a total of 285 subjects will be enrolled. Assuming the missed scanning rate of adjacent important anatomical structures in experimental group is 8%, the missed scanning rate of adjacent important anatomical structures in control group is 20%. Bilateral significance level 5% (alpha =5%), assurance 80% (beta =20%), shedding rate 10%, Expected to enroll 285 patients in total.

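### The primary missed scanning rate is defined as a mean count of missed structures per examination, but the 285 patients are planned as 8% versus 20% with one yes/no outcome each

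*Combined protocol and SAP*

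**What the plan says.** Section 4.1 gives one primary endpoint, the missed scanning rate of important structures next to the pancreas, and defines it so: "It was calculated by dividing the number of important anatomy that is not scanned in the actual EUS pancreas by the number of EUS". Section 4.2, item 5, uses the same form by station: "It was calculated by dividing the number of important anatomy that is not scanned in the different standard stations by the number of EUS".

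Several structures per examination are evidently intended. The Introduction (Section 2) gives landmarks as examples, "Such as organs (kidney, spleen), blood vessels (such as splenic artery, splenic vein, portal vein), ducts (pancreatic duct, bile duct), etc", which names seven and leaves the list open. Under Study Process, the synopsis states: "The recorder shall record the number of adjacent important structures, the number of standard stations, the operation time and the lesion detection etc".

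Section 8.4 sets the planning values: "Assuming the missed scanning rate of adjacent important anatomical structures in experimental group is 8" per cent, and "the missed scanning rate of adjacent important anatomical structures in control group is 20" per cent. The other inputs are "Bilateral significance level 5% (alpha =5%), assurance 80% (beta =20%), shedding rate 10" per cent, for 285 patients in total. Section 6.5.1 allocates 1:1. Section 8.4 names no formula, number of structures per examination, standard deviation or within-patient correlation. Sections 8.2, 8.3 and 8.5 name no test for the primary endpoint.

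**The concern.** The numerator counts structures and the denominator counts examinations. One examination can add several misses to the numerator but only one unit to the denominator, so the result is an average count with no ceiling at 100%. The planning values are percentages, and the sample size appears to treat them as the probability of a single yes/no event per patient.

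Three different endpoints fit the text to some degree: a mean count per examination, the proportion of patients with any structure missed, and the proportion of required structures missed. Each has its own variance, test and power. Since the plan names neither a test nor a fixed list of structures, the choice could be made after the data are seen. A figure computed literally by Section 4.1 also could not be read against the planned 8% and 20%.

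**Working it through.** **Inputs from the documents.** Rates 0.08 and 0.20 (difference 0.12), two-sided 5%, power 80%, 10% dropout (Section 8.4); 1:1 allocation (Section 6.5.1). Normal quantiles are 1.960 and 0.8416, and (1.960 + 0.8416)² = 7.849.

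**Step 1: reproduce 285.** Assume one yes/no outcome per patient.
- Unpooled variance: n = 7.849 × (0.20×0.80 + 0.08×0.92) / 0.12² = 7.849 × 0.2336 / 0.0144 = 127.3, so 128 per arm. Then 256/0.9 = 284.4, so **285**. This is an exact match.
- Pooled variance: 130.1, so 131 per arm; 262/0.9 = 291.1, so 292.
- Arcsine: 125.4, so 126 per arm; 252/0.9 = 280.

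The arithmetic behind 285 is sound for a binary outcome. The steps below hold 128 evaluable per arm fixed and vary what the rates mean.

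**Step 2: literal Section 4.1, mean counts of 0.08 versus 0.20.** Take the variance as φ times the mean (φ is assumed; φ = 1 is Poisson). Power = Φ(0.12/√(φ×0.28/128) − 1.960).
- φ = 1: 0.12/0.04677 = 2.566, giving 72.8%. For 80% power, n = 7.849×0.28/0.0144 = 152.6, so 153 per arm; 306/0.9 = 340 enrolled.
- φ = 1.5: 55.4%. φ = 2: 44.2%.
- Simulation (20,000 runs, unequal-variance z test) gives 74.3%, 58.3% and 48.1% for φ = 1, 1.5 and 2.

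A whole-number count with mean p below 1 has variance of at least p(1−p), reached only when no examination has more than one miss. On this reading, 80.2% (Step 3) is therefore the upper limit of the formula.

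**Step 3: patients with any structure missed, 8% versus 20%.** Unpooled: 0.12/√(0.2336/128) = 2.809, giving 80.2%. The pooled test gives 79.4%. Fisher's exact test, if that were chosen, gives 75.3%.

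**Step 4: share of structures missed, 8% versus 20%, patient as the unit.** The variance of a patient's share is p(1−p)(1+(k−1)ρ)/k, with k structures and within-patient correlation ρ. Both are assumed; k = 7 is borrowed from the Introduction's examples.

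| k | ρ | Power (unpooled) |
|---|---|---|
| 7 | 1 | 80.2% |
| 7 | 0.7 | 90.3% |
| 7 | 0.5 | 96.1% |
| 7 | 0.3 | 99% |
| 6 | 0.5 | 95.7% |
| 15 | 0.5 | 97.0% |

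Pooled-variance figures are lower by less than one percentage point. Here 80.2% is the lower limit, reached only when a patient's structures are all missed or all seen together.

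**Step 5: what Section 4.1 would report under Step 4.** With seven structures, the formula returns 7×0.08 = 0.56 and 7×0.20 = 1.40, a control rate of 140%.

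**Step 6: the two percentage readings are not interchangeable.** If 8% and 20% are per-structure rates and seven structures are independent, the proportion of patients with any miss is 1 − 0.92⁷ = 44% versus 1 − 0.80⁷ = 79%.

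**The case against.** The strongest reply is that this is a drafting slip. All six definitions in Section 4.2 end by dividing by the number of examinations, so the phrase may have been reused and the true denominator lost. Section 8.4 speaks in percentages, and under either percentage reading a normal-approximation test has about 80% power or more at the planned size. The low figures come from the count reading, which percentages do not suggest, and the variance ratios of 1.5 and 2 have no source in the documents.

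Much of this stands. A share of structures may well be what was meant, in which case 285 is adequate, and the count figures show sensitivity rather than an expected shortfall. The seven structures are illustrative only. A fixed list may exist in the case report form, to which Section 7.1 refers and which is not among the documents; exclusion criterion 7 in Section 3.2 also hints at a defined set.

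It does not rescue the text. Items 1, 2 and 4 of Section 4.2 put patients in the numerator, while Section 4.1 and item 5 put structures there, so the document does word the two differently. Even if a slip is granted, the intended endpoint could be either of two quantities with different planning rates, and nothing in the protocol says which.

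**Conclusion.** The concern holds. The primary endpoint as written is a mean count per examination, and the sample size was reproduced exactly only as a comparison of two proportions with one yes/no result per patient. Nothing reconciles them.

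At 128 evaluable per arm the power is at most about 80% if the endpoint is the literal count (73% under Poisson variance), about 80% for patients with any miss, and at least about 80% for the share of structures (90% to 99% with seven structures and correlation 0.7 to 0.3). These are normal-approximation figures. The variance ratio, the correlation and the number of structures are assumptions. The finding is not that the trial is too small. It is that the stated 80% is not attached to the endpoint as defined, and this must be settled before analysis because it concerns the only primary endpoint.

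**What to change.** - **Sections 4.1 and 4.2, item 5:** choose one endpoint and define it. The natural choice is missed structures divided by structures required, where the denominator is a fixed, listed set of k structures per examination times the number of examinations. The alternative is the proportion of patients with any listed structure missed.
- **Analysis:** name the test. If structures are counted, keep the patient as the unit, through per-patient proportions or a binomial GEE with patient-level robust standard errors. Treating structures as independent would make the confidence interval too narrow.
- **Section 8.4:** say what 8% and 20% refer to, justify them for the chosen endpoint (they cannot simply be carried from one percentage reading to the other), name the formula, and restate the power of the existing 285, with k and the correlation given as assumptions.
- **If the count per examination is kept:** state the planned means and variance and recalculate. About 340 enrolled would be needed for a Poisson count of 0.08 versus 0.20.

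The cost is a wording amendment, one checklist and one power calculation. The synopsis already has the number of structures recorded. If the case report form does not record which structures were missed, it needs a small change too. Under either percentage reading the planned 285 can probably stand, subject to the test chosen.
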